2.3 Study endpoints

Main endpoints and definitions:

This study primarily evaluates the proportion of patients with YWHAB

high expression locally advanced rectal cancer who achieve tumor downstaging (ypTNM 0-I stage) after neoadjuvant therapy with mFOLFOX6 combined with Citrus Flavonoid Tablets (Aimianlang). The tumor downstaging rate (ypTNM 0-I stage) refers to the percentage of patients with locally advanced rectal cancer who, after receiving neoadjuvant chemotherapy with mFOLFOX6 or mFOLFOX6 + Citrus Flavonoid Tablets (Aimianlang), have their postoperative pathological stage of the surgical specimen classified as ypTNM 0-I stage.

Secondary endpoints and definitions:

- (1) The degree of pathological remission is defined as follows: ① Complete Remission (CR): All tumor target lesions have disappeared, no new lesions have appeared, and tumor markers are normal, lasting at least 4 weeks. ② Partial Response (PR): The sum of the maximum diameters of tumor target lesions has decreased by at least 30%, lasting at least 4 weeks. ③ Stable Disease (SD): The sum of the maximum diameters of tumor target lesions has not decreased by more than PR, or increased by less than PD. ④ Disease Progression (PD): The sum of the maximum diameters of tumor target lesions has increased by at least 20%, or new lesions have appeared.
- (2) The 3-year disease-free survival rate (DFS) is the proportion of patients who have not experienced any of the following events from the start of randomization to the end of year 3: disease progression, surgical gross/microscopic tumor residue, local recurrence, distant metastasis, or death for any reason, whichever occurs first.
- (3) Overall survival time (OS) is the time from randomization to death for any reason.
- (4) Tumor regression grading TRG: TRG 0 means no residual tumor cells, TRG 1 means a single cell or a small group of cells; TRG 2 means residual cancer with a proliferative response to connective tissue; TRG 3 means minimal evidence of tumor response.
- (5) Safety indicators, treatment-related adverse reaction rate (grade III and

above): Antitumor drugs/therapy In clinical trials, drug adverse reactions determined to be related to drug therapy at grade III and above, excluding nonspecific infusion reactions.

3. Selection and withdrawal of subjects

3.1 Inclusion criteria:

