4.1 Study treatment grouping

This study is a prospective, open-label, double-arm, Phase II clinical trial that includes a neoadjuvant treatment group using the mFOLFOX6 regimen and a neoadjuvant treatment group combining the mFOLFOX6 regimen with Citrus Flavonoid Tablets (Aimalang). The study aims to enroll patients with locally advanced rectal cancer who are in clinical stage I, II, or III. Endoscopic biopsy specimens will be collected for YWHAB immunohistochemical testing to identify patients with high YWHAB expression in locally advanced rectal cancer. These patients will then be randomly assigned to either the mFOLFOX6 treatment group or the mFOLFOX6 combined with Citrus Flavonoid Tablets (Aimalang) treatment group for neoadjuvant therapy. The mFOLFOX6 regimen involves 4-6 cycles before surgery and 6-8 cycles after surgery, with each cycle lasting 14 days: on day 1, 85 mg/m² of oxaliplatin is administered intravenously over 180 minutes; on day 1, 400 mg/m² of leucovorin is administered intravenously over 120 minutes; and on day 1, 2400 mg/m² of 5-fluorouracil is administered continuously intravenously for 46 hours. The Citrus Flavonoid Tablets (Aimalang) treatment regimen involves taking 500mg of Citrus Flavonoid Tablets (Aimalang) orally three times daily, with doses given on days 1-14 of each 14-day cycle.

This trial allows for dose adjustments. Patients who experience disease progression during neoadjuvant therapy may stop the study treatment and directly undergo surgery or follow local guidelines. If a patient cannot tolerate the planned 6 cycles of neoadjuvant therapy, early surgery can be considered. Any patient who has received another anticancer regimen before surgery will stop the study treatment and be managed according to local guidelines. The postoperative

treatment for both groups is determined by the investigator, which may include continuing the mFOLFOX6 regimen combined with Citrus Flavonoid Tablets (Aimalang). It is important to note that all patients in the control group are prohibited from taking Citrus Flavonoid Tablets (Aimalang) without authorization during the trial. If a patient needs to take this medication for any reason, they should consult their primary physician, who will decide whether to use an alternative or discontinue the patient's participation in the trial.

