5.3 End of treatment/exit from study visit

When the subject has completed the study treatment/exited the study, relevant assessments and examinations are required. They should be performed as follows:

- Weight and ECOG score;
- Life signs: pulse, respiratory rate, body temperature and blood pressure;
- Comprehensive physical examination: general condition, head and face, skin, lymph nodes, eyes, ear, nose and throat, oral cavity, respiratory system, cardiovascular system, abdomen, reproductive and urinary system, musculoskeletal, nervous system and mental state;
- Complete blood count: red blood cell count, hemoglobin, platelet count,

white blood cell count, neutrophil count and lymphocyte classification count;

- Routine urine: white blood cells, red blood cells, proteinuria; if proteinuria is greater than or equal to 2+, 24-hour urine protein quantification should be added;
- Blood biochemical: ALT, AST, γ -GT, TBIL, DBIL, AKP, BUN or urea (preferably BUN), TP, ALB, Cr, GLU, K+, Na+, Ca2+, Mg2+, Cl-;
- Tumor markers;
- Coagulation function: activated partial thromboplastin time (APTT), prothrombin time (PT), thrombin time (TT), fibrinogen (FIB), international normalized ratio (INR);
- 12. Lead electrocardiogram: attention should be paid to QT, QTc and P-R intervals. If there are abnormalities, other relevant tests should be done according to the investigator's judgment;
- Document adverse events.

5.4, follow-up period

The survival follow-up period ends when the subject dies, is lost to follow-up, withdraws from informed consent and refuses to continue providing information, or the sponsor terminates the study. During this period, a visit is conducted every three months through telephone or other effective methods to collect survival information and details about subsequent anti-tumor treatments (if the subject starts new anti-tumor treatment, the treatment plan and its duration should be recorded).

For subjects without imaging evidence of disease progression, imaging assessments should continue to be conducted at the frequency specified in this study until the subject experiences disease progression, death, loss to follow-up, withdrawal of informed consent and refusal to continue providing information, initiation of other anti-tumor treatments, or termination of the study by the sponsor. Every effort should be made to obtain imaging evidence of disease

progression in these subjects.

6. Effectiveness evaluation

6.1 Effectiveness parameters:

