The main efficacy indicator of this study was the proportion of patients in each treatment group who achieved tumor downstaging (ypTNM 0-I stage), and the secondary efficacy indicators were the proportion of patients with complete pathological remission, 3-year disease-free survival (DFS), overall survival time (OS) and tumor regression grade TRG.

6.2 Evaluation criteria of effectiveness:

This study evaluated the proportion of patients with YWHAB high expression locally advanced rectal cancer who achieved tumor downstaging (ypTNM 0-I stage) in neoadjuvant treatment with mFOLFOX6 combined with citrus flavonoid tablets (Aimalang).

- (1) Downstaging rate of tumor (ypTNM 0-I stage): the proportion of patients with locally advanced rectal cancer who received mFOLFOX6 or mFOLFOX6 combined with citrus flavonoid tablets (Aimalang) as neoadjuvant chemotherapy, and the proportion of patients with postoperative pathological stage of ypTNM 0-I stage in surgical specimens.
- (2) The degree of pathological remission is defined as follows: ① Complete Remission (CR): All tumor target lesions have disappeared, no new lesions have appeared, and tumor markers are normal, lasting at least 4 weeks. ② Partial Response (PR): The sum of the maximum diameters of tumor target lesions has decreased by at least 30%, lasting at least 4 weeks. ③ Stable Disease (SD): The sum of the maximum diameters of tumor target lesions has not decreased by more than PR, or increased by less than PD. ④ Disease Progression (PD): The sum of the maximum diameters of tumor target lesions has increased by at least 20%, or new lesions have appeared.

Subjects who did not meet the primary endpoint criteria are included in the denominator but not in the numerator.

- (3) When determining the disease-free survival (DFS), clinical deterioration without clear evidence of disease progression according to the RECIST 1.1 criteria is not considered a disease progression. For subjects who died without prior reported disease progression, it is considered that the disease progressed at the time of death. Subjects who have neither experienced disease progression nor died will be censored at their last evaluable tumor evaluation date. Independent central imaging review will be conducted to confirm the independent central imaging service provider of the subject, which will receive all images from the research center and assess the subject's disease progression according to the RECIST 1.1 criteria.

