8.1 Analysis of population

- Informed Consent Set ICS: This analysis set will include all subjects who have signed an informed consent form.
- Intention-to-treat (ITT) analysis set: According to the principle of intention-to-treat analysis, all patients who were randomly assigned to the group at the time of randomization were analyzed according to the group into which they were assigned. This analysis set is the main analysis set for

efficacy endpoints.

- The Full Analysis Set (FAS) is defined as the group of all participants who were enrolled and received at least one dose of the study drug, following the intention to treat (ITT) principle. In analyses based on the FAS, participants are included according to their assigned group at enrollment, regardless of the actual treatment they received;
- In line with the protocol analysis set (Per-Protocol Set, PPS), ITT patients who did not experience significant protocol deviations that affected the efficacy assessment were included. The PP population was used for sensitivity analysis of the primary and key secondary efficacy endpoints.
- Safety set (Safety Set, SS): Will include all subjects who have received at least one study drug treatment. The safety set is the primary population for safety analysis.

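### The disease-free survival definition has no event for a primary tumour that is never resected, and sections 2.3(2) and 6.2(3) disagree on residue found at surgery

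*Combined protocol and SAP*

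**What the plan says.** Section 2.3, secondary endpoint (2), defines the 3-year DFS rate as "the proportion of patients who have not experienced any of the following events from the start of randomization to the end of year 3". The events are "disease progression, surgical gross/microscopic tumor residue, local recurrence, distant metastasis, or death for any reason, whichever occurs first".

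Section 6.2(3) gives the rules for applying it. Progression needs imaging evidence: "clinical deterioration without clear evidence of disease progression according to the RECIST 1.1 criteria is not considered a disease progression". Everyone else falls under a censoring rule: "Subjects who have neither experienced disease progression nor died will be censored at their last evaluable tumor evaluation date". Surgical residue is not mentioned there.

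Section 8.1 defines the ITT set as all randomised patients and says of it: "This analysis set is the main analysis set for" efficacy endpoints. Section 8.3 analyses DFS by Kaplan-Meier, log-rank and Cox.

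The plan foresees patients who may not reach surgery. Section 4.1 states: "Any patient who has received another anticancer regimen before surgery will stop the study treatment and be managed according to local guidelines". A patient who progresses during neoadjuvant therapy "may stop the study treatment and directly undergo surgery or follow local guidelines". Section 3.3 allows withdrawal for adverse events or general deterioration, and 4.2.1 ends participation when toxicity does not resolve in time. Among the points at which 5.4 ends scheduled imaging is "initiation of other anti-tumor treatments, or termination of the study by the sponsor".

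**The concern.** The event list plainly means persisting tumour to be a failure, but it ties that failure to an operation. A patient whose whole primary stays in place, because of refusal, unfitness or a change of treatment, can have no DFS event at all. The clock starts at randomisation and the main analysis set is ITT, so such patients belong to the DFS analysis and need a rule.

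Two things are at stake. First, the reported 3-year DFS would include people who were never free of disease. Second, the trial is open-label and the two sections disagree about residue. If the scoring of these patients is settled only after outcomes are known, that choice could itself introduce bias.

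**Working it through.** The plan states no DFS rate, hazard ratio or event count, so there is no figure to reproduce. The check compares the two rules and then scales the gap on stated assumptions.

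**1. The rules side by side**

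| Patient | Section 2.3(2) | Section 6.2(3) |
|---|---|---|
| Never resected, stable primary, no metastasis, alive | No listed event: disease-free | No progression or death: censored at last evaluable scan |
| Resected with gross or microscopic residue, no progression, alive | Event | Censored |
| RECIST progression, metastasis or death | Event | Event |

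For the first patient, each listed event fails in turn. A stable or shrinking primary is not progression, residue needs an operation, local recurrence presupposes removal, and there is neither metastasis nor death. Metastasis enters 6.2(3) as a new lesion, which the plan's own response definitions count as progression. Residue has no such route.

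The second row is a contradiction between the two sections. The sentence in 6.2 that keeps non-achievers in the denominator concerns the primary endpoint only and does not help here.

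**2. Size for the 2.3(2) proportion**

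Three inputs are assumed, because the documents give none of them:
- u: share of randomised patients never resected, with tumour still present (2%, 5%, 10%)
- q: share of those with no listed event at 3 years (25%, 50%, 75%)
- S: 3-year DFS in everyone else

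Rate under the present list: (1 − u)S + uq. 
Rate if non-resection is an event: (1 − u)S. 
Overstatement: uq, whatever S is.

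| u | q = 25% | q = 50% | q = 75% |
|---|---|---|---|
| 2% | 0.5 points | 1.0 | 1.5 |
| 5% | 1.25 | 2.5 | 3.75 |
| 10% | 2.5 | 5.0 | 7.5 |

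Taking the 236 in section 8.5 as the total randomised, this reclassifies between 236 × 0.02 × 0.25 = 1.2 and 236 × 0.10 × 0.75 = 17.7 patients across both arms.

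**3. Size in Kaplan-Meier**

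If these patients are censored early, for instance because other treatment starts and imaging stops, the curve estimates S. Counting them as early events gives (1 − u)S, so the gap is uS. At S = 70% this is 1.4, 3.5 and 7.0 points for u = 2%, 5% and 10%. Over S = 60-80% the ranges are 1.2-1.6, 3.0-4.0 and 6.0-8.0 points.

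**4. Direction between arms**

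Under the present list, an arm's rate changes with u at the rate q − S. At S = 70% and q = 25%, it falls from 69.1% (u = 2%) to 65.5% (u = 10%). At q = 75%, it rises from 70.1% to 70.5%. With early censoring it stays near S whatever u is. An arm with more unresected patients may therefore look worse, about the same or marginally better.

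**The case against.** The strongest reply is that the affected group is narrow: unresected, tumour present, no RECIST progression, no metastasis, alive. Section 5.4 continues imaging in patients without progression and asks for every effort to document it, so many of these patients would become later events rather than lost ones. A tumour found inoperable at operation and left behind is arguably gross residue and already counted. DFS is secondary and does not drive the sample size. All of this stands, and it limits the weight of the point. It does not supply the missing rule. The imaging safeguard also lapses when other anti-tumour treatment starts, and such censoring is plausibly informative.

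A reader might infer three stronger claims that the documents do not support:
- *The unresected patient is a 3-year success in every analysis.* That is exact only for the 2.3(2) proportion. In the Kaplan-Meier analysis the patient is event-free until censored.
- *An unresected patient always scores better than one with a positive margin.* That holds under 2.3(2), but 6.2(3) read literally censors both.
- *The 10% dropout in 8.5 caps the non-resection rate.* It is a sample-size allowance, and nothing links it to surgery.

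A blanket event would also be wrong for a patient managed without surgery after a complete clinical response, who may truly be disease-free. The fix has to allow for this.

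**Conclusion.** The omission is real, and no other section repairs it. Followed as written, the plan classifies a patient with an untouched primary as disease-free in the 3-year proportion, and as event-free until censored in the time-to-event analysis. Separately, 2.3(2) and 6.2(3) contradict each other on surgical residue.

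The size cannot be determined from the documents. The 0.5-7.5 points for the 3-year proportion rest entirely on the assumed 2-10% never resected and 25-75% of those without a listed event at 3 years. A reader might go on to infer that the arm with more unresected patients is favoured. Step 4 of the working shows that this does not follow, and the direction of any between-arm bias is uncertain. This is a modest correction to a secondary endpoint.

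**What to change.** Use one identical DFS event list in 2.3(2) and 6.2(3). It should include gross or microscopic residue at surgery and a new event: *primary tumour not resected, with tumour still present*. Reword the censoring sentence in 6.2(3) so that it applies to patients with none of the listed events.

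Date the new event at a single pre-specified time from randomisation, the same in both arms. Using the date of the decision not to operate would make an unblinded judgement set the event time. The chosen time must be late enough that a delayed but completed resection is not counted. A patient with an earlier listed event keeps the earlier date.

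Patients with a documented clinical complete response, by criteria fixed in advance, stay in follow-up without an event. Add one sensitivity analysis without the new event, and report the number never resected in each arm.

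The cost is a short edit in two sections, a dating convention and response criteria to settle beforehand, and one extra analysis. Reported 3-year DFS will be slightly lower. Treatment, visits and sample size do not change.

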4.1 Study treatment grouping

This study is a prospective, open-label, double-arm, Phase II clinical trial that includes a neoadjuvant treatment group using the mFOLFOX6 regimen and a neoadjuvant treatment group combining the mFOLFOX6 regimen with Citrus Flavonoid Tablets (Aimalang). The study aims to enroll patients with locally advanced rectal cancer who are in clinical stage I, II, or III. Endoscopic biopsy specimens will be collected for YWHAB immunohistochemical testing to identify patients with high YWHAB expression in locally advanced rectal cancer. These patients will then be randomly assigned to either the mFOLFOX6 treatment group or the mFOLFOX6 combined with Citrus Flavonoid Tablets (Aimalang) treatment group for neoadjuvant therapy. The mFOLFOX6 regimen involves 4-6 cycles before surgery and 6-8 cycles after surgery, with each cycle lasting 14 days: on day 1, 85 mg/m² of oxaliplatin is administered intravenously over 180 minutes; on day 1, 400 mg/m² of leucovorin is administered intravenously over 120 minutes; and on day 1, 2400 mg/m² of 5-fluorouracil is administered continuously intravenously for 46 hours. The Citrus Flavonoid Tablets (Aimalang) treatment regimen involves taking 500mg of Citrus Flavonoid Tablets (Aimalang) orally three times daily, with doses given on days 1-14 of each 14-day cycle.

This trial allows for dose adjustments. Patients who experience disease progression during neoadjuvant therapy may stop the study treatment and directly undergo surgery or follow local guidelines. If a patient cannot tolerate the planned 6 cycles of neoadjuvant therapy, early surgery can be considered. Any patient who has received another anticancer regimen before surgery will stop the study treatment and be managed according to local guidelines. The postoperative

treatment for both groups is determined by the investigator, which may include continuing the mFOLFOX6 regimen combined with Citrus Flavonoid Tablets (Aimalang). It is important to note that all patients in the control group are prohibited from taking Citrus Flavonoid Tablets (Aimalang) without authorization during the trial. If a patient needs to take this medication for any reason, they should consult their primary physician, who will decide whether to use an alternative or discontinue the patient's participation in the trial.

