2.1 Overall design of the study

This study is a prospective, open, double-arm, phase II clinical trial to explore the mFOLFOX6 combined with citrus flavonoid tablets (Aimalang) regimen as neoadjuvant therapy for YWHAB high expression locally advanced rectal cancer. The study design is in accordance with ethical requirements.

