- (1) Histopathology was diagnosed as rectal adenocarcinoma, all other histological types were excluded, and the colonoscopy report or clinical physical examination suggested the presence of hemorrhoids;
- (2) The clinical pathological stage of the tumor is T3-4 or N+ and M0; 8th edition AJCC TNM staging, Appendix 1)
- (3) Immunohistochemical staining of tissue samples showed that YWHAB was highly expressed in rectal cancer patients;
- (4) The age of obtaining informed consent is 18-75 years old;
- (5) Eastern United States Cooperative Group Physical Status Score (ECOG) was 0-1 points (refer to Appendix 3);
- (6) No previous systemic anti-tumor treatment for rectal cancer, including cytotoxic drugs, immune checkpoint inhibitors, molecular targeted therapy, endocrine therapy, etc.;
- (7) Based on the following laboratory test values obtained during the screening period, appropriate organ function is present: white blood cell count $\geq 3 \times 10^9/L$, neutrophil count $\geq 1.5 \times 10^9/L$, platelet count $\geq 75 \times 10^9/L$, serum total bilirubin $\leq 1.5 \times$ upper limit of normal (UNL), aspartate aminotransferase or alanine aminotransferase $\leq 2.5 \times$ UNL, serum creatinine $\leq 1.5 \times$ UNL;
- (8) Women of childbearing age must have a negative serum pregnancy test within 3 days prior to the start of study medication and be willing to use a medically recognized effective contraceptive method (e.g., IUD, pill, or condom) during the study and for 3 months after the last dose of study medication;

- (9) For male subjects whose partner is a woman of reproductive age, effective contraception was used during the study and for 3 months after the last study dose;
- (10) The subject has given his/her own consent and signed an informed consent form, and the subject is willing and able to comply with the planned visits, research treatment, laboratory tests and other trial procedures.

3.2 Exclusion criteria:

- (1) Whole body CT, MR or PET-CT (at least including chest, whole abdomen and pelvis) confirmed distant metastasis;
- (2) Whole genome testing for DPD enzyme deficiency or 7/7 homozygotes for UGT1A1*28 locus in patients;
- (3) The patient has complete intestinal obstruction, active bleeding or perforation and requires emergency surgery;

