4.3.2 Other anti-tumor treatment and experimental drugs

During the study treatment, the subject will not be allowed to receive other anti-tumor treatments not specifically specified in this protocol. Other systemic anti-tumor treatments will not be allowed.

5. Research process

5.1, Screening period

After the patient signs the informed consent form, they enter the screening phase. Endoscopic biopsy specimens from patients with locally advanced rectal cancer are collected for YWHAB immunohistochemical testing to identify those with high YWHAB expression, and these patients are selected for inclusion in the study. Before signing the informed consent, patients undergo routine laboratory tests and imaging assessments as required by clinical practice. If the relevant data is available within the specified time window, it can be utilized.

The following screening should be completed within 28 days prior to the start of study drug therapy:

- Obtain informed consent signed by the subject;

- Collect demographic data: name, sex, date of birth, height, weight, etc.;
- Collect adverse events: record adverse events from the time of signing informed consent;
- Tumor diagnosis: date of pathological confirmation, pathological grading, clinical imaging staging (TNM), clinical staging, etc.;
- History of cancer treatment;
- Imaging examination: enhanced CT of chest, abdomen and pelvis;
- The YWHAB immunohistochemical detection was performed on the endoscopic biopsy specimens.
- (Non-essential) Specify the KRAS exon 2 codons 12 and 13, exon 3 codons 59 and 61, exon 4 codons 117 and 146, NRAS exon 2 codons 12 and 13, exon 3 codons 59 and 61, exon 4 codons 117 and 146, and BRAF V600E gene status;
- (Mandatory) MMR/MSI detection of tumor tissue;
- The following screening should be completed within 7 days prior to the start of study drug therapy:
 - Weight and ECOG score;
 - Life signs: pulse, respiratory rate, body temperature and blood pressure;
 - Comprehensive physical examination: general condition, head and face, skin, lymph nodes, eyes, ear, nose and throat, oral cavity, respiratory system, cardiovascular system, abdomen, reproductive and urinary system, musculoskeletal, nervous system and mental state;
 - Complete blood count: red blood cell count, hemoglobin, platelet count, white blood cell count, neutrophil count and lymphocyte classification count;

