8.3 Efficacy analysis and statistical methods

For the proportion of patients in each treatment group who achieved tumor downstaging (ypTNM 0-I stage), the proportion of participants with pathological complete remission, and the tumor regression grading (TRG), statistical analysis was conducted using mean values and standard deviations. For the three-year disease-free survival rate and overall survival time, Kaplan-Meier curves were plotted, and the 95% confidence interval for the median time was calculated using the Brookmeyer Crowley method. The Log-rank test was used to compare differences between groups, and the hazard ratios (HR) for each endpoint were

estimated using the Cox proportional hazards model, exploring the impact of factors other than treatment on these endpoints. Additionally, the number and percentage of cases that occurred at each endpoint, as well as the number and percentage of censored cases, were calculated and categorized by censoring reason.

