8.5 Sample size determination

This study primarily focuses on the rate of tumor downstaging (ypTNM 0-I stage) in each treatment group. Based on current data, after

neoadjuvant chemotherapy with mFOLFOX6, approximately 35% of locally advanced rectal cancer patients achieve tumor downstaging (ypTNM 0-I stage). Among these, about one-third (n=90) of YWHAB high-expressing locally advanced rectal cancer patients achieved a tumor downstaging rate of about 25%, while about two-thirds (n=90) of YWHAB low-expressing locally advanced rectal cancer patients achieved a tumor downstaging rate of about 43%. It is estimated that the tumor downstaging rate for YWHAB high-expressing patients receiving mFOLFOX6 combined with citrus flavonoid tablets (Aimalang) neoadjuvant chemotherapy is 40%, with a significance level of 0.05, an efficiency of 0.8, and a dropout rate of 10%. The sample size was estimated to be 236 using PASS V15 software.

Ethical considerations

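### Baseline clinical T and N stage is collected but not planned for use in randomisation or in the ypTNM 0-I comparison, which gives up a modest amount of precision

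*Combined protocol and SAP*

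**What the plan says.** - **Design.** Section 2.1: "This study is a prospective, open, double-arm, phase II clinical trial". Section 4.1: "These patients will then be randomly assigned to either the mFOLFOX6 treatment group" or to the combination group. Neither section, nor any other, gives an allocation ratio, a method of sequence generation or a stratification factor.
- **Entry stage.** Section 3.1, criterion 2: "The clinical pathological stage of the tumor is T3-4 or N+ and M0". Section 4.1 gives a different range, clinical stage I, II or III.
- **Baseline data.** The screening list in 5.1 includes "clinical imaging staging (TNM), clinical staging, etc".
- **Primary endpoint.** Section 2.3 defines it as a surgical specimen staged ypTNM 0-I, yes or no.
- **Primary analysis.** For this proportion, pathological complete remission and TRG, 8.3 says "statistical analysis was conducted using mean values and standard deviations". It names no test, confidence interval, stratified estimate or covariate. Other factors enter only through the Cox model for DFS and OS, and they are not named. Section 8.4 refers to a statistical analysis plan for safety detail only.
- **Sample size.** Section 8.5 assumes 25% against 40%, "with a significance level of 0.05, an efficiency of 0.8, and a dropout rate of 10" per cent, and arrives at 236. It does not state whether the test is one- or two-sided.

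**The concern.** The outcome is T and N stage after treatment, so T and N stage before treatment is the natural prognostic covariate. Patients entering under T3-4 or N+ start at different distances from ypTNM 0-I. If stage I patients are also enrolled, as 4.1 says, they start inside the target range.

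If such a covariate is left out of both randomisation and analysis, the standard error is larger than it need be. A chance difference in stage mix then also passes uncorrected into the one estimate the trial produces. Because the trial is open-label, deciding on adjustment only after an imbalance has been seen would be hard to defend.

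**Working it through.** **Inputs from 8.5.** Rates 0.25 and 0.40; difference 0.15; alpha 0.05; power 0.80; dropout 10%; total 236. With 1:1 allocation (assumed, since no ratio is given) that is 118 per arm.

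**The plan's own figure.** The unpooled variance term is 0.25×0.75 + 0.40×0.60 = 0.4275, and 0.4275/0.15² = 19.
- One-sided: (1.645 + 0.842)² × 19 = 117.5, so 118 per arm and 236 in total, before any dropout allowance.
- Two-sided: (1.960 + 0.842)² × 19 = 149.1, so 150 per arm, 300 in total, and 334 after dividing by 0.9.

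So 236 is reproduced only as a one-sided calculation without dropout. Both kinds of test are shown below.

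**Unadjusted comparison, 118 evaluable per arm.** SE = √(0.4275/118) = 0.0602, or 6.0 points; the 95% half-width is 11.8 points. Then 0.15/0.0602 = 2.492. Two-sided power is Φ(2.492 − 1.960) = 70%; one-sided power is Φ(2.492 − 1.645) = 80%.

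**Adjusted comparison.** The documents give no stage-specific rates and no stage mix, so these are assumptions. Let q be the share in the more advanced stage group (0.5 to 0.7) and g the gap in ypTNM 0-I rate between stage groups (10 to 35 points), with the same treatment difference in each group. The only prognostic gap in the documents is 43% − 25% = 18 points, for YWHAB low against high in 8.5. It is not a stage effect and serves only as a sense of scale.

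Standardising over stage removes q(1−q)g² from the variance term of each arm:

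variance ratio = 1 − 2q(1−q)g²/0.4275

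For q = 0.5 and g = 0.35 this is 1 − 0.06125/0.4275 = 0.857.

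| Gap g | Variance ratio (q = 0.7 to 0.5) | Two-sided power | One-sided power |
|---|---|---|---|
| none (unadjusted) | 1 | 70% | 80% |
| 10 points | 0.990 to 0.988 | 71% | 81% |
| 20 points | 0.961 to 0.953 | 72% | 82% |
| 30 points | 0.912 to 0.895 | 74-75% | 83-84% |
| 35 points | 0.880 to 0.857 | 76-77% | 84-85% |

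If the treatment effect is instead a common odds ratio, the gains are slightly larger: two-sided power is 71-77% for gaps of 10 to 30 points and at most about 80% at 35 points.

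With 10% loss (106 per arm) the unadjusted starting points fall to 66% two-sided and 76% one-sided. The variance ratios do not change.

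**Chance imbalance without stratification.** The 95% limit on the between-arm difference in stage share is 1.96 × √(2q(1−q)/118), which is 11.7 points at q = 0.7 and 12.8 points at q = 0.5. Multiplied by g, the shift in the unadjusted difference at that limit is 0.117 × 10 = 1.2 points at the low end and 0.128 × 35 = 4.5 points at the high end.

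**These are one effect, not two.** At q = 0.5 and g = 0.35 the variance of that shift is 0.06125/118, exactly the amount that adjustment removes from 0.4275/118. The imbalance is already part of the 6.0-point SE.

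**The case against.** The strongest reply is that randomisation makes an unadjusted comparison valid. Type I error holds over repeated randomisations and the SE already carries the variation in stage mix. That stands. A reader might infer that the primary result would be biased by stage; the documents do not support it, and the point is about precision and the credibility of one realised result.

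A reader might also infer that the sponsor has chosen simple randomisation and an unadjusted test. The documents are silent on the allocation method and name no between-arm test for ypTNM 0-I. Those are gaps in the plan, and stage adjustment comes after filling them.

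The size is wholly assumed. At a 10-point gap the gain is under one point of power. The 35-point gap with half the patients advanced implies control rates of 42.5% and 7.5%, an odds ratio of about 9, which is a strong effect. The gain therefore runs from negligible to modest.

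Finally, a simple stage II against III split would separate node-negative from node-positive patients only, would ignore T stage, and would leave no place for the stage I patients in 4.1. That objection is sound, and the factor has to be built from both T and N.

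**Conclusion.** The concern holds as a low-cost improvement, not as a threat to validity. The plan records a baseline variable of the same kind as its primary endpoint and assigns it no role in randomisation or in the primary comparison.

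Across the assumed gaps of 10 to 35 points, the cost of leaving it unused is about 1% to 14% of the variance of the risk difference. In power this is 1 to 7 percentage points two-sided and 1 to 5 one-sided. A chance imbalance at its 95% limit would move the estimate by roughly 1 to 4.5 points, against a target of 15 and an SE of 6.

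The omission itself can be read directly from the text. Its size rests on assumed stage effects, 1:1 allocation and 118 evaluable patients per arm. A reader might hope that adjustment rescues the power stated in 8.5. Under a constant treatment difference it does not: two-sided power at 118 per arm reaches 77% at best. The sample-size shortfall is a separate matter.

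**What to change.** 1. Reconcile the stage range in 3.1 (T3-4 or N+, M0) with that in 4.1 (stage I, II or III). No stage factor can be defined until the two agree.
2. In 8.3, name the primary comparison: the difference in ypTNM 0-I proportions in the ITT set with its 95% CI, stratified by or standardised over prespecified baseline clinical T and N categories. Mantel-Haenszel weighting, or logistic regression with marginal standardisation, would serve. State whether the test is one- or two-sided, and report the unadjusted difference as supportive.
3. In 4.1, stratify randomisation by the same clinical stage factor, with few enough levels that no stratum is sparse in a trial of 236.

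The stratification factor must be fixed before the first patient is randomised, and the analysis wording before any outcome data are seen. The cost is the randomisation specification and a paragraph in 8.3. No extra patients, visits or measurements are needed.
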